[figure not shown]
PROTOCOL: HMD-VR trial – Head Mounted Display Virtual Reality trial

Title

Cognitive load and performance in immersive virtual reality versus conventional virtual reality training of laparoscopic surgery - a randomized trial

Trial flow chart

This trial follows the CONSORT-statement for randomized trials.¹²

List of abbreviations

CAMES: Copenhagen Academy for Medical Education and Simulation

CLT: Cognitive Load Theory

CVR: Conventional Virtual Reality

HMD: Head Mounted Display

IVR: Immersive Virtual Reality

VR: Virtual Reality

Background

During the last three decades, minimally invasive surgery and laparoscopic procedures have become widespread due to several advances compared to conventional, open surgery: such as a reduction of the surgical trauma, shorter hospitalization and faster postoperative recovery¹. However, laparoscopic surgery requires other skills than open surgery, partly because the surgeon has to overcome the fulcrum effect, the limited degrees of freedom and the loss of depth perception due to 2D projection. These psychomotor skills need to be learned and trained, preferably, in a risk-free environment such as virtual reality (VR) simulation or other simulation-based training.

VR simulation is increasingly implemented in laparoscopic skills training programs, as it is well known to improve surgical trainees' operating performance and decrease their operating time².

Opponents of VR simulation often raise concerns that there is a substantial gap between the simulation-environment and the real-life operating room³. The effect of this being that skills obtained in VR simulation may not be transferable to the operating room. New technology may improve this by using VR head-mounted displays (HMDs) in combination with VR laparoscopic simulators. The result is an immersive VR (IVR) simulation experience where the surrounding environment from the real OR is integrated in the simulation, which may increase the transferal of skills as the environment in the simulation approaches the real-life environment.

An increase in the realism of simulations, e.g. IVR, might also increase the strain on the trainees' working memory and might lead to an overload of the trainees' cognitive abilities. This, according to cognitive load theory (CLT), will inhibit learning and a measurement of cognitive load is therefore of value when experimenting with IVR-training. CLT is used to optimize simulations-based training programs by examine how the cognitive load affects the actual learning. CLT is based on an information-processing model of the human cognitive architecture⁴, which posits that information sensed from the environment must be processed by working memory before it can be consolidated and stored in long-term memory in the form of schemas⁴. Most literature on CLT considers three different types of cognitive load:

- Intrinsic load is a direct function of the complexity of the performed task and the expertise of the learner.
- Extraneous load is a result of superfluous processes that do not directly contribute to learning.
- Germane load is caused by learning processes that deal with the intrinsic load such as schema formation⁴

The different sources of cognitive loads are mainly considered additive, and if the sum surpasses working memory capacity, it can result in overloading. Such

cognitive overload hinders learning as excessive intrinsic and extraneous load takes up capacity from the germane load (i.e. actual learning). A goal of educational designers is to optimize germane load and decrease extraneous load.

Up until now, investigations of the use of IVR simulation in medical education are meagre. Huber et al.⁵ found IVR simulation of laparoscopy to be clinical and technical feasible. Interestingly, they report that participants had longer operating time and higher error rates during IVR than during VR simulation of the same tasks. In the framework of CLT, a plausible explanation for this finding could be an increased extraneous load of the IVR simulation environment compared with conventional VR simulation. In another study, a significantly higher cognitive load was found in the more complex dissection environment compared with VR simulation for the mastoidectomy procedure⁶. To our knowledge, no study has previously investigated the role of cognitive load in IVR laparoscopic training.

We hypothesize that IVR increases cognitive load compared with conventional virtual reality (CVR) simulation of laparoscopic surgery. In this study, we examine the cognitive load and performance of a laparoscopic procedure in IVR and CVR in a randomized, controlled setup. The results will potentially have implications for organization of future training.

Primary objective

To compare immersive virtual reality (IVR) simulation training using a head-mounted display with virtual reality laparoscopic simulation training on LapSim (CVR) with regards to cognitive load.

Secondary objectives

To compare immersive virtual reality (IVR) simulation training using a head-mounted display with virtual reality laparoscopic simulation training on LapSim (CVR) with regards to performance

To investigate side effects of IVR simulation training such as motion sickness, feeling of immersion etc.

Setting and time

The study will be conducted at the Simulation Centre at Copenhagen Academy for Medical Education and Simulation, Rigshospitalet, Denmark, from February to May 2018.

Participants and equipment

Participants are recruited by inviting newly graduated doctors.

Inclusion criteria

- Obtained medical license
- Residents working in Denmark
- Signed informed consent

Exclusion criteria

- Previous participation in trials involving laparoscopic training
- Having performed one or more laparoscopic procedures as primary surgeon, including supervised procedures
- No informed consent
- Does not speak Danish on a conversational level

Participant discontinuation and withdrawal

A participant, who no longer wishes to participate in the trial, can withdraw his/her informed consent at any time. Analyses will be performed according to the intention-to-treat principle where all randomised participants will be analysed. Therefore it is in the interest of the trial to collect as much data from each participant as possible, so the amount of 'missing data' is minimized. If a participant withdraws, the investigator will ask if his/her data may be used in the analyses. Only if the participant specifies, his/her data cannot be used in the analyses, will a new person be randomised. The investigator can discontinue a participant from the trial if the participant does not comply with the training protocol.

Study design

All participants will first complete a questionnaire on background demographics.

Next, all participants will receive a 1-hour of introduction to the laparoscopic simulator, where they will train four different basic skills tasks (see appendix for descriptions). They will train 12 minutes on each basic skill. Subsequently, they will be introduced to the salpingectomy with an ectopic pregnancy procedure and complete one supervised attempt of this procedure on the LapSim (CVR).

Then the participant will be randomized to continue training in either the HMD-VR (IVR) or the LapSim (CVR) simulation environment. After randomization, participants will perform three attempts of the salpingectomy with an ectopic pregnancy procedure without any guidance. The participant will be allowed a maximum of 20 minutes pr. Attempt.

During the simulations, the cognitive load will be estimated using an external secondary-task measurement of reaction time in hundredths/s using a commercially available reaction timer (American Educational Products LLC, USA) where participants responds to an auditory cue by pressing a foot pedal. Reaction time will be measured in series of four repeated measurements: 1) before and

after the procedure (baseline) and 2) at four different points in time during the simulation, representing two calm phases and two phases with stressors during the IVR simulation and at three calm phases and one phase with a stressor during the CVR simulation.

The IVR simulation will consist of four different videos. The actors in these videos starts and ends in the same positions allowing the videos to be played in any order after one another.

Setup: The assistant to the left is holding the camera, the surgical nurse is opposite and a bit to the left, the floor nurse is at the end of the operating table which is further to the left and the nurse anesthetist is to the right behind the anesthetic cover. The anesthesiologist is not in the operating theatre.

Video 1 (57 seconds) and video 2 (59 seconds):

There will be no talking and the surgical staff will just move slightly around and/or watch the surgeon.

Video 3 (48 seconds):

The anesthesiologist enters and conducts a conversation with the nurse anesthetist then leaves. Simultaneously the phone rings and the floor nurse will be talking on it.

Video 4 (59 seconds):

Secondary reaction time will be used as an estimate of cognitive load and is measured in hundredths second, with a maximal reaction time of 99/100 second. Reaction time during simulation will be calculated relatively to the mean initial baseline reaction time of the individual participant.

The simulator will automatically gather data regarding the participants' performance, measuring:

Total Time (s)

Blood Loss (ml)

Pool Volumen (ml)	Ovary Diathermy Damage (s)
Tube Cut: Uterus Distance (mm)	Bleeding Vessel Cut (max 1)
Left Instrument Path Length (m)	Right Instrument Path Length (m)
Left Instrument Angular Path (degrees)	Right Instrument Angular Path (degrees)

The background questionnaire will include questions on demographics, prior simulation training, prior laparoscopy experience, experience with HMD and video game experience. Finally, a questionnaire regarding motion sickness¹⁰ and the feeling of being immersed during the training will be provided after IVR and CVR simulation training.

Data collection

The primary investigator will collect data, and the data will be pseudo-anonymized and kept in such a way that collected data will be stored separately from the anonymization key.

Statistics/Data analysis

Data will be analyzed using statistical software (SPSS) and relevant statistical methods (linear mixed models). Groups will be compared using independent samples t-test. The level of statistical significance will be set at alpha= 0.05.

Sample size

In general sample size calculations are based on the primary outcomes of 1) relative reaction time and 2) performance metrics, but due to repeated measurements there is no standardized way to estimate the number of participants. Based on similar studies, the authors suggest a total of 48 participants in the trial will be sufficient to detect a difference in reaction time of 5 % and performance of 10 %.

Economic

No external funding has been received.

Ethical considerations

Ethical approval or exemption will be obtained from the Regional Ethical Committee of the Capital Region, Denmark.

Written consent for the participation in the trial will be obtained.

The data involves no patient related information and approval by the Danish Data Protection Agency is not relevant.

The trial will be reported to a clinical trial database.

Publication

The findings of this trial are to be published in a peer-reviewed journal within the field of surgery and/or medical education.

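### Reaction time is analysed relative to a short baseline with no stated model terms; adjusting for that baseline may gain precision and costs at most about 2% in variance

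*Combined protocol and SAP*

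**What the plan says.** The primary objective compares immersive VR (IVR) with "virtual reality laparoscopic simulation training on LapSim (CVR) with regards to cognitive load". The Outcome measures section takes secondary-task reaction time as the estimate of cognitive load and sets the rule for baseline: "Reaction time during simulation will be calculated relatively to the mean initial baseline reaction time of the individual participant". It does not say whether this means a ratio or a difference. The same section says reaction time "is measured in hundredths second, with a maximal reaction time of 99/100 second".

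On the number of readings, the Study design section says: "Reaction time will be measured in series of four repeated measurements". These are taken before and after the procedure, and at four time points in each of three attempts. The stressor content of these time points differs by arm: "two phases with stressors during the IVR simulation and at three calm phases and one phase with a stressor during the CVR simulation". In IVR the remaining two are calm.

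The Statistics/Data analysis section says "Data will be analyzed using statistical software (SPSS) and relevant statistical methods (linear mixed models") and "Groups will be compared using independent samples t-test", at alpha 0.05. It lists no fixed effects, covariates or random effects. Sex stratifies the randomisation (Randomization and blinding section) but is not named in the analysis. The Sample size section expects that "48 participants in the trial will be sufficient to detect a difference in reaction time of 5" per cent.

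**The concern.** Dividing by the baseline assumes that a participant whose baseline is 10% slower will be exactly 10% slower in simulation. On the log scale that is a slope of 1. The baseline mean rests on few readings, so part of its spread between participants is noise, and division passes that noise to all of a participant's values. A model with baseline as a covariate estimates the slope instead. The noisier the baseline, the flatter the slope it uses.

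Precision is at stake. The target difference is small (5%), there are 48 participants, and the baseline readings are collected anyway. There is also a question of prespecification. With no terms listed, the choice between a t-test on relative values and several possible mixed models stays open until the data are seen.

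**Working it through.** **The plan's own figure.** The 48 cannot be reproduced, because no SD, power or sidedness is given. Solving backwards with 24 per arm (1:1 assumed), two-sided alpha 0.05 and 80% power, the implied SD of the relative measure is 5 / [(1.960 + 0.842) × √(2/24)] = 6.18 percentage points. At an SD of 10 points, power would be 41%. The documents do not say which SD is realistic.

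**Inputs for the comparison.** From the documents: 3 attempts × 4 time points, and series of four readings. I take each time point as one series, so 3 × 4 × 4 = 48 simulation readings per person. The initial baseline is taken as one series of four. Assumed: between-person log SD at baseline s_b = 0.20; between-person log SD in simulation s_s = 0.20, 0.25 or 0.30; within-person SD s_w = 0.12 or 0.25; correlation ρ between a person's baseline and simulation levels.

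**Formulas** (log scale, per-person values):
- baseline variance v_x = s_b² + s_w²/4
- simulation variance v_y = s_s² + s_w²/48
- covariance c = ρ·s_b·s_s
- ratio analysis: V_R = v_x + v_y − 2c
- baseline adjustment: V_A = (v_y − c²/v_x) × (1 + 1/44), where the last factor is the cost of estimating one slope with 48 participants

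**Worked case** (s_s = 0.20, s_w = 0.25, ρ = 1):
- v_x = 0.04 + 0.0625/4 = 0.055625
- v_y = 0.04 + 0.0625/48 = 0.041302
- c = 0.04
- V_R = 0.016927
- V_A = (0.041302 − 0.0016/0.055625) × 1.0227 = 0.012823
- V_R/V_A = 1.320, so the ratio has 32% more variance. The slope used by adjustment is c/v_x = 0.72.

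**Results: excess variance of the ratio over adjustment, s_b = 0.20**

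| s_s | ρ | s_w = 0.12 | s_w = 0.25 |
|---|---|---|---|
| 0.20 | 1.0 | +6% | +32% |
| 0.20 | 0.7 | +22% | +47% |
| 0.25 | 0.9 | −2% | +5% |
| 0.25 | 0.7 | +3% | +16% |
| 0.30 | 0.7 | −2% | +3% |
| 0.30 | 1.0 | +76% | −1% |

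The gain vanishes where the slope c/v_x is close to 1 and returns when it is clearly below or above 1. At a slope of exactly 1, V_R/V_A = 1/(1 + 1/44) = 0.978. The most that adjusting can cost is therefore 1/44 = 2.3% in variance. If 48 gave exactly 80% power, that cost would bring it to 79.1%.

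**Checks.** Simulation with 8,000 trials per setting gave 1.058, 1.328, 1.225 and 1.492 for the four equal-SD cases, against 1.058, 1.320, 1.222 and 1.471 from the formula. Simulated power for a true 5% difference, ratio against adjusted, was 0.75 vs 0.77, 0.24 vs 0.30, 0.17 vs 0.19 and 0.13 vs 0.17. Both analyses averaged 4.9% to 5.1%, so neither was biased. In separate simulations with other inputs, a t-test on the raw ratio and one on its log had nearly the same power (for example 0.389 and 0.388), so the log scale is not what drives the result.

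**Model terms.** Videos 1, 2 and 3 last 57, 59 and 48 s. Video 3 therefore runs from 57 + 59 = 116 s to 116 + 48 = 164 s, and the reading at t=130 s falls inside it. At that time the IVR arm has a stressor and the conventional VR (CVR) arm does not. At t=240 s both arms have one. The group difference may thus depend on time point, and the model should allow for this.

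**The case against.** The strongest objection concerns size. The larger gains rest on equal between-person spread at baseline and in simulation. Reaction times during a demanding dual task could plausibly spread more widely; with SDs of 0.25 to 0.30 and correlation 0.7 most of the gain goes. This stands, and a reader who infers that the ratio certainly loses precision goes beyond the documents. What remains is an asymmetry: a loss of at most about 2% against a gain that may be nil or considerable.

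Second, a linear mixed model does not exclude a baseline covariate, so the plan cannot be said to have rejected adjustment. This also stands. But no term is stated, and the only group comparison actually specified is unadjusted.

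Third, the Sample size section names relative reaction time as a primary outcome, so the adjusted contrast changes the summary. That is true. It is still a percent difference between arms, the unit in which the 5% target is set.

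Fourth, power rises by only 2 to 6 points in the four equal-SD cases and does not rescue a weak design. That is fair; the argument is that the gain is almost free.

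A reader might also infer that dividing by baseline biases the comparison. It does not if allocation cannot affect the baseline. Nor do the documents support the inference that the 0.99 s limit hides an IVR effect: they give no reaction-time level and no sign that the limit is reached often.

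**Conclusion.** The concern holds as one of efficiency and prespecification, not of bias. The relative measure with an unadjusted t-test may cost precision: about 6% to 47% excess variance under equal SDs of 0.20 and four baseline readings, and about −2% to +16% with wider simulation SDs at correlation 0.7. All SDs and correlations are assumed, so the size cannot be fixed from the documents and may be nil. The worst case for adjusting, about 2%, depends only on 48 participants and one estimated slope.

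The conclusion has one condition. The Study design section does not say whether the initial baseline is taken before allocation, or whether a headset is worn. A baseline affected by allocation would distort the relative measure and the adjusted analysis alike.

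This should be changed, but it is not a fatal flaw. Confidence is medium.

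**What to change.** 1. State that the initial baseline is taken before allocation, or under identical no-headset conditions in both arms. If neither is so, settle this first.
2. Specify the mixed model already named. The outcome is log reaction time in simulation. Fixed effects are group, log mean initial baseline, sex (the stratification factor), attempt, time point and group by time point. Participant is a random effect.
3. Make the group difference from this model the primary comparison, averaged over attempts and the four time points and back-transformed to a percent difference. It replaces the t-test on the relative value. Report the difference at each time point as well.
4. As a minor addition, say how readings at 0.99 s are handled and report their percentage by arm.

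The cost is analysis-plan wording, one descriptive table and at most about 2% in variance from the baseline slope. Sex is kept near balance by the stratification, and attempt and time point are balanced within participants when readings are complete, so those terms should add little. Baseline and sex are already collected. If step 1 is confirmed, participants and measurements do not change.

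### The group comparison is an independent-samples t-test, which cannot adjust for sex, the one stratification factor, and which is not linked to the mixed models named beside it

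*Combined protocol and SAP*

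**What the plan says.** The Statistics/Data analysis section has three sentences. The first reads "Data will be analyzed using statistical software (SPSS) and relevant statistical methods (linear mixed models" and closes the bracket there, naming no outcome, group term, covariate or random effect. The second is "Groups will be compared using independent samples t-test", without an outcome, a unit of analysis or a covariate. The third sets alpha at 0.05.

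The data are repeated. Under Study design, "After randomization, participants will perform three attempts of the salpingectomy with an ectopic pregnancy procedure without any guidance", and cognitive load is probed at 80, 130, 180 and 240 seconds. The same section says "Reaction time will be measured in series of four repeated measurements", which may mean several readings at each probe. Under Outcome measures, "Reaction time during simulation will be calculated relatively to the mean initial baseline reaction time of the individual participant". The Sample size section acknowledges the repetition, but only to explain why there is no formal calculation: "due to repeated measurements there is no standardized way to estimate the number of participants".

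Randomization and blinding names sex as the single stratification variable and justifies it by a possible effect on initial laparoscopic simulator performance. Sex does not appear in the analysis text.

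**The concern.** Stratifying by sex balances the arms on sex. That balance reduces the true variability of the group difference if sex is related to the outcome. A two-sample t-test does not know this: it leaves the between-sex variation in its error term, so its standard error is too large and its p-values too high on average. The trial would carry out the stratification and then give up the precision it buys. With 48 participants, even a few points of power are worth keeping when the remedy needs no new data.

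The second strand is clarity. Two methods stand side by side with no statement of which answers the primary question. A t-test is valid for these data only on one value per participant, and the plan does not state that unit.

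**Working it through.** **The plan's own figure.** The total of 48 cannot be reproduced, because no standard deviation, power or within-participant correlation is given. At 24 per arm and two-sided 5%, 80% power needs a standardized difference of (1.960 + 0.842) × √(2/24) = 0.81. A 5-point difference then requires the SD of the analysed value to be at most 5/0.81, about 6.2 points. There is little slack if the SD is larger: at an SD of 10, power for 5 points is 41%.

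**Inputs.** From the protocol: 48 participants, alpha 0.05, stratification by sex, three attempts after randomization, four probe times per attempt. Assumed: 1:1 allocation, two-sided testing, balance within sex, and R², the share of the variance of participant means that sex explains. The documents give no R², so a range is shown.

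**Type I error on one mean per participant.** With arms balanced on sex, the true variance of the group difference is (1 − R²) times the variance the unadjusted t-test estimates. Its actual error rate is therefore about 2 × [1 − Φ(1.960/√(1 − R²))].

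**Power.** Fix the effect so that the sex-adjusted test has 80%. The unadjusted test then has power of about Φ(2.802 − 1.960/√(1 − R²)).

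| R² | 1.960/√(1 − R²) | Type I error, formula | Type I error, simulation | Power, formula | Power, simulation |
|---|---|---|---|---|---|
| 0 | 1.960 | 5.0% | 4.9% | 80.0% | 80.2% |
| 0.05 | 2.011 | 4.4% | 4.4% | 78.5% | 78.4% |
| 0.10 | 2.066 | 3.9% | 3.8% | 76.9% | 77.0% |
| 0.20 | 2.191 | 2.8% | 2.8% | 72.9% | 72.7% |

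The simulations used 100,000 trials per setting. The sex-adjusted test held 4.9% to 5.0% type I error and 80.0% to 80.2% power throughout. With 67% women instead of an even split, the results agreed within 0.5 points.

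**Number of values per participant.** If all three attempts are probed at all four times, each participant gives 3 × 4 = 12 in-simulation reaction times, and 3 values of each performance metric. The protocol does not state outright that every attempt is probed, and an attempt that ends before 240 seconds would give fewer.

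**What the unit would change.** In simulation, a t-test on one mean per participant rejected in 4.8% to 5.4% of null trials across the assumed intraclass correlations (ICC). For contrast only, entering m readings per person as independent rows gives 2 × [1 − Φ(1.960/√(1 + (m − 1) × ICC))]. At ICC 0.1 this is 17.6% for m = 12 and 7.4% for m = 3. The plan does not describe that analysis, so these figures are not part of the size of this point.

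**Choice of adjusted method.** In 60 simulated complete data sets, a mixed model (participant and attempt-within-participant random intercepts) and a sex-adjusted linear model on participant means gave the same group estimate to 1e-14. Standard errors differed by a median of 0.001% and at most 6.8%. The sex-adjusted participant-mean test rejected in 4.99% of 100,000 null trials.

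**Intervals at single time points.** These need more care. In simulations with 8,000 trials per setting, participant-by-time-point variance of 0.1, 0.2 or 0.3 (assumed) was present but left out of the model. The nominal 95% interval at 130 seconds then covered about 94%, 94% or 92%.

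**The case against.** The strongest reply is that nothing stated in the plan is invalid. Mixed models, a standard tool for repeated data, are named in the sentence just before the t-test. A fair reading is mixed models for the repeated outcomes and t-tests for the rest. On that reading only a linking sentence is missing. This stands, and it limits the second strand to clarity.

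A reader might infer that readings will be pooled as independent rows, or that twelve separate tests will be run, with false-positive rates far above 5%. The documents do not support that. No sentence describes either analysis, no correlation is given, and the Sample size section shows that the authors knew the measurements were repeated.

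A second reply is that the gain from sex is small and conditional. This also stands in part. At R² of 5% or 10% the loss is two or three points of power, and the error is on the safe side. The rationale concerns initial simulator performance, whereas the outcomes follow an hour of basic-skills training and a supervised attempt, and reaction time is scaled to the participant's own baseline. It does not remove the point: if sex explains nothing, adjusting costs one degree of freedom, and otherwise precision is recovered.

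A third reply is that 130 seconds is a stressor only in IVR, so an average over time points mixes unlike conditions. That is true of a t-test on means and a mixed model alike. It is a reason to show results by time point, not evidence against either method.

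**Conclusion.** The point holds as an improvement to the analysis and not as an error that invalidates it. The only method tied to the group comparison cannot use the only stratification factor. Under assumed R² of 5%, 10% and 20%, with 24 per arm and two-sided testing, type I error falls to about 4.4%, 3.8% and 2.8%, and power to about 78%, 77% and 73% against 80%. At R² of zero there is no loss. The case is best supported for performance; for reaction time a gain is only possible.

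The missing link between the t-test and the mixed models, and the unstated unit, are lack of clarity. It would be wrong to conclude from them that the trial's type I error will be inflated: on one mean per participant it is at or below 5%.

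**What to change.** Replace the t-test sentence with:

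> Relative reaction time is compared between groups with adjustment for sex, using a linear mixed model with a participant random effect and fixed effects for group, attempt, time point, group-by-time point and sex (or, with complete data, one mean per participant in a linear model with group and sex). The primary contrast is the group difference averaged over the four time points. Results at each time point are descriptive, since t=130 is a stressor only in IVR; their intervals come from a sex-adjusted comparison of participant means at that time point, or from a model that allows participant-by-time-point variation. Performance metrics recorded at each attempt are compared in the same sex-adjusted way. The t-test is kept for variables with one value per participant, such as the MSAQ score.

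If the metric listed as "Bleeding Vessel Cut (max 1" with its bracket closed is 0/1, the share of a participant's three attempts can be compared in the same way. Simulated type I error for this was 5.0% to 5.2% (assumed prevalence 15% or 30%, ICC 0.1 or 0.3).

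The cost is one paragraph and one degree of freedom. Sex, group, attempt and time point are already recorded, and SPSS fits these models. One limit remains: the average can mask a difference at 130 seconds or be driven by it, so the time-point results must stand beside it. This wording does not settle how the several performance metrics are to be handled together; that needs its own statement.

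### Performance is a secondary objective, but the Sample size section makes it a second primary outcome, with no named metric, testing order or multiplicity rule

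*Combined protocol and SAP*

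**What the plan says.** - **Title.** It pairs the two outcomes: "Cognitive load and performance in immersive virtual reality versus conventional virtual reality training of laparoscopic surgery".
- **Background.** One hypothesis is stated: "We hypothesize that IVR increases cognitive load compared with conventional virtual reality (CVR) simulation of laparoscopic surgery".
- **Primary objective.** Immersive simulation is to be compared with "virtual reality laparoscopic simulation training on LapSim (CVR) with regards to cognitive load".
- **Secondary objectives.** The first repeats the comparison with "virtual reality laparoscopic simulation training on LapSim (CVR) with regards to performance". The second concerns side effects, including motion sickness and immersion.
- **Sample size.** "In general sample size calculations are based on the primary outcomes of 1) relative reaction time and 2) performance metrics". The total of 48 participants is then called "sufficient to detect a difference in reaction time of 5 % and performance of 10" per cent. No power, SD or metric is given.
- **Outcome measures.** Ten simulator metrics are listed: total time, blood loss, pool volume, ovarian diathermy damage, distance of the tube cut from the uterus, bleeding vessel cut, and path length and angular path for each instrument. None is ranked and no composite is formed.
- **Statistics/Data analysis.** Linear mixed models and independent-samples t-tests are named without being assigned to outcomes. Then: "The level of statistical significance will be set at alpha= 0.05". No sidedness, alpha split, testing order or adjustment is given.

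**The concern.** The same family of outcomes is secondary under the objectives and primary under Sample size. The choice decides what the trial can claim. If performance is secondary, a null reaction-time result is a null trial, whatever the metrics show. If performance metrics are a primary outcome in the plural, with none singled out, any one of ten could carry a positive primary conclusion. The objectives would give a reader grounds to object to such a report, but no statistical rule in the text prevents it.

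A second consequence is that the 10 % target cannot be checked. Elapsed time, a blood volume and a path length can have very different relative SDs, so a 10 % difference means something different for each.

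**Working it through.** **Step 1: the plan's own figure.** The total of 48 cannot be reproduced, because power, SD, sidedness and allocation ratio are not stated. Assume 24 per group, two-sided 0.05 and 80% power. Then the normal approximation, n per group = 2 × (1.960 + 0.842)² × SD² / difference², can be solved backwards. The standardized difference is 2.802 × √(2/24) = 0.809. The implied SD is 5/0.809 = 6.2 percentage points for reaction time and 10/0.809 = 12.4 for performance.

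The same formula run forwards for a 10 % difference, rounding each group up, shows how much depends on the metric:

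| Assumed SD (percentage points) | Total N |
|---|---|
| 10 | 32 |
| 15 | 72 |
| 20 | 126 |
| 30 | 284 |

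**Step 2: false positives over ten metrics.** Two conditions are assumed, neither of which the documents state: each metric is tested once at two-sided 0.05, and any one significant result counts.

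Under independence: 1 − 0.95¹⁰ = 0.401.

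Under a common correlation r, write each test statistic as √r·U + √(1 − r)·E, with U shared and E separate for each metric. With c = 1.960, the chance of at least one rejection is

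1 − ∫ φ(u) [Φ((c − √r·u)/√(1 − r)) − Φ((−c − √r·u)/√(1 − r))]¹⁰ du.

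| Assumed r | Chance of at least one false positive |
|---|---|
| 0.3 | 0.351 |
| 0.5 | 0.287 |
| 0.7 | 0.213 |
| 0.9 | 0.128 |

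The documents give no correlations. Each participant makes three attempts, so further comparisons are possible; they are not counted here.

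**Step 3: what a testing order controls.** Test reaction time once at 0.05, and one named metric at 0.05 only if reaction time is significant. If reaction time has no true effect, any false claim requires a false rejection at the first step, with probability at most 0.05. If reaction time has a true effect, only the named metric can give a false claim, again with probability at most 0.05. The limit covers these two claims and no others.

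**Step 4: what the order costs.** Assume 24 per group and 80% power for each test (standardized difference 0.826 by the noncentral t with 46 degrees of freedom). At correlation 0, both are significant with probability 0.80 × 0.80 = 0.64. Simulation of paired t-tests gives about 0.67 at correlation 0.3 and 0.69 at 0.5.

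**Step 5: the two-primary alternative.** Reaction time and one named metric, each at 0.05 with either sufficing, would give 1 − 0.95² = 0.098 if independent. At 0.025 each the total is at most 0.05. With the same standardized difference of 0.826, power for each falls from 0.80 to 0.706. By the normal approximation, restoring 80% multiplies the group size by (2.241 + 0.842)² / (1.960 + 0.842)² = 1.21. That is 24 × 1.21 = 29.1, so 30 per group or 60 in total.

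**The case against.** The best defence is that this is loose wording in one paragraph. The objectives are explicit, and there is one hypothesis. The sentence in question opens as a general remark and goes on to say that no standard method exists. A trial may be sized for a secondary outcome, so the 10 % target does not by itself make performance primary, and neither does the title. On this view one corrected phrase is enough, and formal error control over secondary metrics in an education trial is a matter of preference.

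Much of this stands. The objectives are the better guide to intent, and the fix follows them. But the paragraph goes on to size this trial on both outcomes, so the general opening does not dispose of the conflict. The numbering of the two outcomes is not a testing order, because both are called primary. Correcting the phrase alone would still leave the 10 % tied to no metric.

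It is also fair to say that the error rates rest on assumed conditions. A reader might infer that the trial will run ten separate tests and accept any one of them, giving a 40% error rate. The documents say neither thing. Independence is implausible for time, path lengths and angular paths from the same attempts, and a single common correlation across such unlike metrics is a simplification.

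**Conclusion.** The contradiction is real and should be resolved before analysis. It concerns what may be claimed about performance. A reader might infer that the cognitive-load result is itself compromised. It is not: one prespecified reaction-time test at 0.05 keeps its error rate. Nor do the documents establish that two primary outcomes were intended; the title leaves this possible and the objectives point the other way.

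The size is conditional. If all ten metrics were tested once at two-sided 0.05 and any one counted, the chance of a false-positive performance finding would be about 13% to 35% at assumed common correlations of 0.9 to 0.3, so more than twice the nominal level even at the low end. The 40% figure applies only under independence. Separately, whether 48 participants suffice for the 10 % target cannot be judged until a metric and its SD are given.

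**What to change.** 1. **Sample size.** Name relative reaction time as the only primary outcome, tested at 0.05, and state the sidedness. The hypothesis is directional, but the plan does not say whether the test is.
2. **Sample size.** Tie the 10 % to one key secondary metric, named by the investigators before analysis and claimed as confirmatory only if the reaction-time test is significant. Total time is one candidate, since the Background cites longer operating time under immersive simulation. However, that sentence equally reports higher error rates, and attempts are capped at 20 minutes, so the choice needs a reason.
3. **Statistics/Data analysis.** Label the other nine metrics, and the motion-sickness and immersion scores, exploratory. The entry "Bleeding Vessel Cut (max 1" looks binary; if it is, analyse it with a method for binary data and not a t-test.

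The 5% limit then covers the reaction-time and key-metric claims only.

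**Cost.** The change is to wording, with no added participants or data, and reaction time keeps its full alpha. The downside is that performance supports no confirmatory claim if reaction time is not significant. Assuming 24 per group and 80% power for each test, both succeed in about 64% to 69% of trials at correlations of 0 to 0.5. The exploratory outcomes support no confirmatory claim at all.

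**Alternative.** If two primary outcomes are intended, the plan should say so in the objectives and test reaction time and one named metric at 0.025 each. That lowers an assumed 80% power to about 71% for each, or needs about 60 participants to keep 80%.
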